Study Population:	Newly diagnosed breast cancer patients with an indication for post-operative radiotherapy after neo-adjuvant chemotherapy and surgery
Accrual Period:	2-3 years
Study Design:	Prospective two cohorts study in newly diagnosed breast cancer patients. Cohort 1 patients will receive Radiation to breast and chest wall. Cohort 2 patients will receive Radiation to Breast, chest wall and Level III/SCV nodes.
Study Duration:	Patients will complete treatment in three weeks (15 fractions). All patients will be followed at 3 months after the completion of treatment then yearly for the next 5 years.
Study Agent/ Intervention Description:	Cohort 1 (Post-segmental Mastectomy, post-mastectomy and Post-mastectomy with expanders or final reconstruction): Prone whole breast or chest wall 3D-CRT or IMRT at 2.7 Gy X 15 fractions (40.50 Gy) with a concomitant boost of 0.50 Gy (7.5 Gy) to the original tumor bed in post-segmental mastectomy patients or mastectomy scar in post-mastectomy patients. Patients who have undergone reconstruction will not receive concomitant boost.
	Cohort 2: In addition to receiving radiation to the original tumor bed, patients will also receive radiation to Level III axillary nodes and Supraclavicular nodes: 3D-CRT or IMRT at 2.7 Gy X 15 fraction (40.50 Gy) If clinically indicated, internal mammary nodes will also be treated and a supine set up will be used

[figure not shown]
Primary Objective: *Acute Toxicity: Grade 2-3 dermatitis <25% in each cohort*

Secondary Objective: *QOL, defined by RTOG-PRO; Late toxicity, Fibrosis, Telangiectasia, Brachial Plexopathy.*

Exploratory Objectives: *Local control; Time to Progression, Survival; Evaluation of Determinants of Breast Fibrosis*

SCHEMA

Stage I-III Breast Cancer Patients, Eligible For Post-Surgical Radiotherapy After Neo-adjuvant Chemotherapy And/Or Hormonal Therapy Followed By Segmental Mastectomy Or Mastectomy

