*** Radiation fields and doses:**

Cohort 1

- a) Post segmental mastectomy: Prone whole breast 3D-CRT or IMRT at 2.7 Gy X 15 fractions (40.50 Gy) with a concomitant boost of 0.50 Gy (7.5 Gy) to the tumor bed.
- b) Post-mastectomy: Prone whole breast 3D-CRT or IMRT at 2.7 Gy X 15 fractions (40.50 Gy) with a concomitant boost of 0.50 Gy (7.5 Gy) to the mastectomy scar on the chest wall.
- c) Post-mastectomy with expanders or final reconstruction: Prone whole breast 3D-CRT or IMRT at 2.7 Gy X 15 fractions (40.50 Gy).

Cohort 2

Either a, b, c +

- d) Level III axillary nodes and Supraclavicular nodes: 3D-CRT or IMRT at 2.7 Gy X 15 fractions (40.50 Gy) -If clinically indicated, internal mammary nodes will also be treated and a supine set up will be used.

All patients will be followed for toxicity and outcome (local and systemic recurrence, survival) In addition, patients will complete a self-assessment of QOL at baseline, completion of radiation treatment, at 45-60 day follow-up and at 2 year follow-up.

TREATMENT SCHEMA

Within a month from initiation	Week 1	Week 2	Week 3	Months 3	Months 12-24-36-48-60
simulation	RT	RT	RT	Follow up	Follow up
Patient education - baseline QOL Blood sample			QOL assessment Blood sample	QOL assessment	QOL assessment

STUDY SYNOPSIS

Patients undergoing primary systemic therapy, followed by surgery often receive post-operative radiation. While the targets treated post-operatively vary and depend on the initial and post-surgical stage, patients generally undergo 6-7 weeks of daily (Monday to Friday) post-operative radiation.

This approach is long and draining, particular in this population of breast cancer patients who often experience chemotherapy-induced fatigue. Our group has developed and tested a combined positioning and hypo-fractionated regimen of post-operative radiotherapy that may be particularly convenient and indicated for these women.

Specifically a prone set-up has enabled safe sparing of heart and lung while targeting the breast and, more recently, level III and supraclavicular nodes.

While we have extensively tested this approach in the classical adjuvant setting of breast cancer, until now we have not tested it after neo-adjuvant chemotherapy.

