4.0 Correlative Studies Background

4.1 Quality of Life Assessment

Patients' quality of life assessments will be performed at regular intervals (baseline, last week of radiation treatment, 45-60 days from starting radiotherapy and 2-year follow-up). QOL will be evaluated in several ways.

First, cosmetic results will be examined using the Breast Cancer Treatment Outcome Scale (BCTOS) using patient self-reports. This brief self-report instrument has high reliability and validity, and has been used in a variety of previous studies on recovery from breast cancer treatment. [14] The BCTOS also will be used as a primary measure to assess breast-related symptoms and treatment effects. Specifically, the BCTOS will be augmented with a brief set of additional items that focus on radiotherapy-relevant symptoms (e.g., reports of skin problems, tenderness/pain in the breast, and hardness in the breast due to enhanced fibrosis). Second, we will use the MOS SF-36 Vitality Scale, a widely used measure with high reliability and validity, will assess fatigue. [15-16]

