13.0 Study Calendar

Study	Pre Treatment	Weekly	Last week	Post Treatment (day 45-60)	Post Treatment (once/year)
History & Physical	X				
Toxicity evaluation	X	X		X	X
CBC with differential	X	X			
Comprehensive metabolic	X	as clinically indicated			
Mammogram and/or breast MRI ^a	X				X
Lumpectomy pathology report	X				
BREAST-focused exam, KPS	X	X		X	X
Blood for TGF-BETA polymorphisms	X		X ^b		
Quality of Life Questionnaires ^c	X		X	X	X
LENT/SOMA assessment					X ^c

- a. Standard mammogram or MRI for both breasts.
- b. Last day of treatment, after last dose of radiation
- c. QOL will be assessed using the Breast Cancer Treatment Outcome Scale (BCTOS) [30] MOS SF- 36 Vitality Scale (see appendix 4) at baseline, last week of radiation treatment, 45-60 days from starting radiotherapy and 2 year follow-up.
- d. Patients will be seen after completion of treatment (at day 45-60) and then yearly for five years to assess long term sequelae by LENT/SOMA scale.

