Appendix 3.2 Quality of Life questionnaire used for follow-up visits

Form QLF(01-25-2005)

Quality of Life Questionnaire - Follow-up

Page 1 of 6

Patient Initials ,
 Last First Middle

Patient Study ID

For patients who receive both radiation and chemotherapy, this should be completed at day 45-60 following start of radiation and at 2-year follow-up.

Patients who experience a documented cancer recurrence or second primary cancer are not expected to complete questionnaires after that event. Patients who discontinue therapy for other reasons are expected to complete all the quality of life assessments.

The first page is to be completed by a clinical staff member. Fill in the items listed on this page, print the patient's study ID at the top of pages 2 through 6 and the assessment time point at the bottom of pages 1 through 6 and give the questionnaire to the patient for completion. After the patient has completed the questionnaire, verify that the date has been recorded at the top of page 2.

Please administer the questionnaire at an office visit if possible. If that is not possible, mail the questionnaire to the patient, then call to ask for the patient's responses over the phone. If all efforts to administer the scheduled questionnaire fail, a B-39 QMD form should be submitted instead.

Institution Name / Affiliate Name		
/		
Staff Member Administering Form		
Last Name	First Name	Phone
Are data amended?  Yes (If yes, circle the amended items.)		
This form is being filled out: (Mark one.)		
 By participant in doctor's office  By clinical staff, on phone with participant  By participant not in doctor's office  Other		

Mark Circles Like This: → ●

assessment time point	 last week RT	 day 45-60	 2 years
-----------------------	------------------------------------	---------------------------------	-------------------------------

Record the assessment time point and participant's Study ID on each of the remaining pages before giving the questionnaire to the participant.

Patient Study ID Date this questionnaire is completed:
Month Day Year*(For example, if you were completing the questionnaire on September 8, 2004, you would write 09 08 2004 in the boxes.)*

Thank you for completing this questionnaire.

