Appendix 3.3 Form for missing Quality of Life information

Form QMD (01-25-2005)

Page 1 of 1

Missing Data Form for Quality of Life Questionnaire

Submit this form whenever a protocol-scheduled Quality of Life (QOL) Questionnaire (i.e., Form QLT, QLP, or QLF) is not filled out by the patient and the assessment cannot be obtained by phone or mail. No missing data form is required for partially completed QOL forms or patients who have died or had a documented breast cancer recurrence or a second primary cancer.

Patient Initials	 ,  	Last	First	Middle	Patient ID	
Institution Name / Affiliate Name _____ / _____						
Person Completing Form		Last Name		First Name		Phone
Today's Date	  Month	  Day	   Year			
Are data amended? (check box if yes, and circle amended items)  Yes						

Time Point for this Form (mark one)
 
 Form QLT: Last week of radiation therapy
 
 Form QLP: 45-60 days after starting radiation therapy
 
 Form QLF: 2 years after adjuvant therapy (radiation and/or chemotherapy)
	

Reason QOL was Not Assessed During Clinic Visit (Mark the main reason and add comments below.)
 
 Staff oversight or understaffing
 
 Staff concerned for patient's medical or emotional condition
 
 Patient stated that she was too ill or upset to complete questionnaire
 
 Patient refused to complete questionnaire for reason other than illness or upset
 
 Patient was unavailable (e.g., scheduling or transportation difficulties)
	
Reason QOL was Not Obtained by Phone or Mail (Mark all that apply and add comments below.)
 
 Staff oversight or understaffing
 
 Patient's medical or emotional condition
 
 Patient refused to complete questionnaire
 
 Staff was unable to contact patient by phone
 
 Questionnaire was mailed to patient but she did not return it (for any reason)

Comments
 <hr/> <hr/>	

Mark Circles Like This: → ●

REFERENCES

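### The staff instruction on the follow-up QOL form leaves out the last-week-of-radiation assessment for patients with radiation and chemotherapy, contradicting the protocol's QOL schedule and the form's own tick-box

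*Combined protocol and SAP*

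**What the plan says.** **Schedule in the protocol body.** Section 4.1 sets the QOL assessments at "baseline, last week of radiation treatment, 45-60 days from starting radiotherapy and 2-year follow-up". Note c of the Study Calendar (section 13.0) repeats this: "at baseline, last week of radiation treatment, 45-60 days from starting radiotherapy and 2 year follow-up". The schema text under Radiation fields and doses says that "patients will complete a self-assessment of QOL at baseline, completion of radiation treatment, at 45-60 day follow-up and at 2 year follow-up". None of these makes an exception for patients who had chemotherapy.

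**Follow-up form.** Form QLF in Appendix 3.2 is the only follow-up questionnaire in the protocol. Its cover page, which clinical staff complete, says: "For patients who receive both radiation and chemotherapy, this should be completed at day 45-60 following start of radiation and at 2-year follow-up". The same page has a time-point box with three options, the first being the last week of radiotherapy, and the box recurs on later pages. The page adds: "Patients who discontinue therapy for other reasons are expected to complete all the quality of life assessments".

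**Missing-data form.** Appendix 3.3 lists three forms. The first is "Form QLT: Last week of radiation therapy". The second is a Form QLP at 45-60 days after radiation starts. Form QLF is listed for the two-year assessment alone.

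**Population.** The Protocol Summary describes the study population as "Newly diagnosed breast cancer patients with an indication for post-operative radiotherapy after neo-adjuvant chemotherapy and surgery". The schema and the title also admit neoadjuvant hormonal therapy.

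**Endpoint.** Section 16.1.2 lists, as a secondary endpoint, QOL measured before, in the course of, and after treatment.

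**The concern.** The sentence on Form QLF is a working instruction to the person who hands out the questionnaire, and it conflicts with the schedule that the form is meant to serve. It singles out patients with both radiation and chemotherapy, who on the protocol's own description of its population are the usual case.

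The last-week assessment is the only QOL measurement taken during treatment, so nothing else supplies the middle part of the section 16.1.2 endpoint. It also bears on the study's rationale: the Study Synopsis argues that a long radiotherapy course is draining for women already fatigued by chemotherapy, and section 4.1 measures fatigue with the SF-36 Vitality Scale.

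If the sentence were followed, the loss would depend on systemic therapy. Last-week results would then come disproportionately from hormone-only patients, and a comparison with baseline or with day 45-60 would mix a change over time with a change in who was measured.

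**Working it through.** The plan states no sample size, power or precision for QOL, so there is no figure to reproduce. The check sets the sources side by side.

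| Source | Applies to | Last week or end of RT | Day 45-60 | 2 years |
|---|---|---|---|---|
| Schema text | all patients | yes | yes, no anchor given | yes |
| Section 4.1 | all patients | yes | from start of RT | yes |
| Study Calendar, note c | all patients | yes | from start of RT | yes |
| Appendix 3.1, time-point box | all patients | yes | from start of RT | yes |
| Appendix 3.2, staff sentence | RT plus chemotherapy | **not named** | from start of RT | yes |
| Appendix 3.2, time-point box | all patients | yes | yes, no anchor given | yes |
| Appendix 3.3 | all patients | yes, as Form QLT | yes, as Form QLP | yes, as Form QLF |

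**Does another form cover the gap?** No. The table of contents lists a baseline form, a follow-up form and a missing-data form under Appendix 3, and nothing else. QLT and QLP exist only as labels.

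**Can the day 45-60 form stand in for the last week?** Hardly. The vitality, pain and symptom items ask about the past four weeks (28 days). Section 7.2 puts radiation at 19-21 days.
- Completed on day 45 from start: recall begins at 45 − 28 = day 17, so it covers only the last few treatment days.
- Completed on day 60 from start: recall begins at 60 − 28 = day 32, after treatment has ended.

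**How many forms are at risk?** Let N = 74 (section 16.3), c = share of patients with chemotherapy, and f = share of those for whom staff apply the sentence as exclusive. Forms at risk = N × c × f. The documents give neither c nor f. With f = 1, the worst case:

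| Assumed c | At risk (74 × c) | Remaining (74 × (1 − c)) |
|---|---|---|
| 50% | 37 | 37 |
| 80% | 59 | 15 |
| 95% | 70 | 4 |

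With f = 0, where staff follow the calendar, nothing is lost at any c.

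**The day 45-60 anchor.** Section 4.1, note c and the forms in Appendices 3.1 to 3.3 count from the start of radiation wherever they state an anchor. Note d counts from completion, the Protocol Summary gives follow-up at 3 months after completion, and the Treatment Schema places a QOL assessment at month 3. With 19-21 days of treatment, day 45-60 after completion is day 64 (45 + 19) to day 81 (60 + 21) from start. That does not overlap day 45-60 from start.

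**The case against.** A reader might infer that the form directs most patients to skip the end-of-radiation questionnaire. The documents do not support that, for four reasons.

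- The sentence names two time points but does not say that they are the only ones. The form's box offers the last week first, so the form is internally inconsistent and not a clear order to omit the visit.
- The schema, section 4.1 and the calendar schedule the assessment for everyone, and Appendix 3.3 expects a missing-data form when it is not obtained. A site working from the calendar would collect it.
- The sentence does not say whether chemotherapy given before surgery counts. The forms look carried over from another study: they are dated 2005 and mention randomization in a non-randomized trial, and Appendix 3.3 speaks of adjuvant therapy. If adjuvant chemotherapy was meant, the sentence might reach few patients here.
- Section 1.2 frames the QOL objective as baseline and after treatment, which the other visits serve. QOL carries no stated hypothesis or power.

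All four points limit what can be claimed about the likely loss. They do not remove the contradiction. In a trial that requires earlier systemic therapy and excludes concurrent chemotherapy other than anti-HER2 agents, reading the sentence to include neoadjuvant chemotherapy is natural. The missing-data form is a weak safeguard: it is triggered only by a questionnaire that the protocol schedules, and staff who take the sentence as the schedule would not file one. Section 16.1.2 also goes beyond section 1.2 by including QOL during treatment.

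**Conclusion.** The staff sentence on Form QLF contradicts the QOL schedule for all patients and the form's own time-point box, and Appendix 3.3 adds form names that have no form behind them. Staff relying on the sentence, and counting neoadjuvant chemotherapy, could miss the only on-treatment QOL assessment in chemotherapy patients and keep it in hormone-only patients.

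The size is unknown. The range of 37 to about 70 of 74 forms rests on assumed chemotherapy shares of 50% to 95% and on every site applying the sentence as exclusive, so it is a worst case and not a forecast. That most patients would in fact miss the assessment cannot be shown.

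The consequence is possible non-random missing data in one secondary endpoint. The primary dermatitis endpoint and the weekly toxicity evaluations do not depend on this form. The point should be corrected because the wording is operative, version 5.0 added two enrolling sites that would work from it, and a missed last-week questionnaire cannot be recovered later.

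**What to change.** 1. In Appendix 3.2, replace the sentence with wording such as: *Every patient, whatever systemic therapy she received, completes this form in the last week of radiation, 45 to 60 days after radiation starts, and at the two-year visit.* The start-of-radiation anchor is kept on purpose, because it is the one on the present form, in section 4.1 and in calendar note c.
2. In Appendix 3.3, label all three time points as Form QLF and remove QLT and QLP, including from the form's introductory text.
3. Reconcile the day 45-60 anchor with calendar note d, which counts from completion, and with the Protocol Summary and Treatment Schema, which give 3 months.
4. Send sites a short memo. In the QOL report, give the number of last-week forms due and received by type of neoadjuvant therapy, so that any loss already incurred is visible.

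The cost is one sentence, a few labels and a memo. No visit is added, since patients attend Monday to Friday in the last week of treatment.

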Appendix 3.3 Form for missing Quality of Life information

Form QMD (01-25-2005)

Page 1 of 1

Missing Data Form for Quality of Life Questionnaire

Submit this form whenever a protocol-scheduled Quality of Life (QOL) Questionnaire (i.e., Form QLT, QLP, or QLF) is not filled out by the patient and the assessment cannot be obtained by phone or mail. No missing data form is required for partially completed QOL forms or patients who have died or had a documented breast cancer recurrence or a second primary cancer.

Patient Initials	 ,  	Last	First	Middle	Patient ID	
Institution Name / Affiliate Name _____ / _____						
Person Completing Form		Last Name		First Name		Phone
Today's Date	  Month	  Day	   Year			
Are data amended? (check box if yes, and circle amended items)  Yes						

Time Point for this Form (mark one)
 
 Form QLT: Last week of radiation therapy
 
 Form QLP: 45-60 days after starting radiation therapy
 
 Form QLF: 2 years after adjuvant therapy (radiation and/or chemotherapy)
	

Reason QOL was Not Assessed During Clinic Visit (Mark the main reason and add comments below.)
 
 Staff oversight or understaffing
 
 Staff concerned for patient's medical or emotional condition
 
 Patient stated that she was too ill or upset to complete questionnaire
 
 Patient refused to complete questionnaire for reason other than illness or upset
 
 Patient was unavailable (e.g., scheduling or transportation difficulties)
	
Reason QOL was Not Obtained by Phone or Mail (Mark all that apply and add comments below.)
 
 Staff oversight or understaffing
 
 Patient's medical or emotional condition
 
 Patient refused to complete questionnaire
 
 Staff was unable to contact patient by phone
 
 Questionnaire was mailed to patient but she did not return it (for any reason)

Comments
 <hr/> <hr/>	

Mark Circles Like This: → ●

REFERENCES

